### 7.1 Recruitment

Both Chief investigator and co-investigators identify the suitable operating list. Then the suitable patients will be identified based on the scheduled surgical procedure. Only those patients meeting the inclusion criteria will be approached.

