### 7.2 Consent

Participants will be given enough time to read the patient information leaflet (minimum of 2 hours). Once they have read the information, any questions will be answered. If they agree for the study, they will be asked to complete the consent form. The consent will be obtained by chief investigator, coinvestigator or one of the research team member, supervised by one of the investigator.

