### 7.3 Randomisation scheme

Randomisation for this study will be completed on a 1:1 basis via sealed envelopes. The Statistician will create 2 master randomisation lists for each site and the envelopes will be numerically ordered.

On arrival to the anaesthetic room, sealed envelope will be opened to reveal the group. Based on the group, following induction of general anaesthesia, the chosen supraglottic airway device will be inserted. Once the supraglottic airway device placement confirmed, tracheal intubation is completed using Fiberoptic scope.

The randomisation will determine which supraglottic airway device to choose. Rest of the process is similar in both groups.

In theatre once the envelopes have been opened the randomisation log will need to be completed. The envelopes containing the assigned device will be retained in a folder in theatre.

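### Section 7.3 keeps the opened, numbered envelopes in theatre without access limits; if the site lists are blocked, recruiters who read them could predict many next allocations

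*Combined protocol and SAP*

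**What the plan says.** Section 7.3 of the combined protocol and SAP sets out the whole scheme. "Randomisation for this study will be completed on a 1:1 basis via sealed envelopes", and "The Statistician will create 2 master randomisation lists for each site and the envelopes will be numerically ordered". The second sentence can be read as one list per site or two. The envelope is opened late: "On arrival to the anaesthetic room, sealed envelope will be opened to reveal the group". The record follows: "In theatre once the envelopes have been opened the randomisation log will need to be completed". The last sentence of the section is "The envelopes containing the assigned device will be retained in a folder in theatre".

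The document gives no method of generating the sequence (simple or blocked), no block size, and no rule on who may see the log or the folder.

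On who recruits, section 7.1 says "Both Chief investigator and co-investigators identify the suitable operating list", and section 7.2 says "The consent will be obtained by chief investigator, coinvestigator or one of the research team member, supervised by one of the investigator". Section 7.3 also makes clear that the operator acts on the known allocation: "Based on the group, following induction of general anaesthesia, the chosen supraglottic airway device will be inserted".

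**The concern.** Sealing, numbering and late opening protect the allocation of the patient now in the anaesthetic room. They do not stop someone from predicting the next allocation out of the past ones, before the next patient is approached. For that, a recruiter needs a visible history and a sequence with enough restriction for the history to be informative. Section 7.3 positively provides for the first, because a folder of opened, numbered envelopes is an ordered record of every allocation at that site. On the second it is silent.

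The stake is selection bias in the primary comparison. Section 2.1 states a directional hypothesis, that intubation is easier and quicker through the I-gel. The primary outcome in section 3.3 is a time that depends on the patient's airway. Mallampati score, thyromental distance, mouth opening and neck movement (section 7.5) can all be judged before surgery. An investigator who expects a given device next could approach or defer a patient accordingly, without intending to bias the result.

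**Working it through.** **Inputs from the document.** Allocation is 1:1 by site (section 7.3). The planned size is 180 across 2 sites (Trial Summary). The document gives no significance level, power or SD from which to rebuild the 180. This point does not dispute that figure and uses it only for scale.

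**Assumptions.** Fixed blocks of 2, 4 or 6, or an unrestricted list. A reader of the folder who sees every past allocation, knows the block size, and guesses the device used less often so far in the block. 90 patients per site and 90 per arm. A two-sided 5% two-sample comparison of intubation time.

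**Step 1: how much can be guessed.** In a block of 2 the first guess is right half the time and the second is certain: (0.5 + 1)/2 = 0.750. In a block of 4 the four guesses are right with probability 1/2, 2/3, (1/3 × 1 + 2/3 × 1/2) = 2/3, and 1. The sum is 2.833, and 2.833/4 = 0.708. The same recursion for a block of 6 gives 4.1/6 = 0.683.

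Allocations known with certainty are 1/2 = 50% for blocks of 2, 1.333/4 = 33.3% for blocks of 4, and 1.5/6 = 25% for blocks of 6. That is 90, 60 and 45 of 180. One balanced list of 90 per site gives 56.1% correct and 2.2% certain. An unrestricted list gives 50% and 0%, even with the whole history in view.

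**Step 2: what a guess could do.** Let g be the share guessed correctly. Suppose selection moves a patient's intubation time by +δ or −δ SD according to the guess, and by nothing when the block is tied. The false difference between arms is then 2δ(2g − 1) SD. The standard error of the difference is √(1/90 + 1/90) = 0.149 SD. With z = bias/0.149, the two-sided type I error is about Φ(z − 1.96) + Φ(−z − 1.96).

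| Block | g | Bias, δ = 0.25 | z | Type I error | Bias, δ = 0.125 | z | Type I error |
|---|---|---|---|---|---|---|---|
| 2 | 0.750 | 0.250 | 1.68 | 39% | 0.125 | 0.84 | 13% |
| 4 | 0.708 | 0.208 | 1.40 | 29% | 0.104 | 0.70 | 11% |
| 6 | 0.683 | 0.183 | 1.23 | 23% | 0.092 | 0.61 | 9% |

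Simulation of 2 × 90 patients with a t-test gives slightly lower values at δ = 0.25 (about 38%, 27% and 22%), because the shift itself adds some variance. At δ = 0.125 it agrees to within about one percentage point. Unrestricted lists stay at about 5% in both cases.

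**Step 3: what removing the folder achieves.** In simulation, a guesser who knows only about a third of past allocations (an assumption, for example one anaesthetist's own cases) is right about 53% of the time under a blocked list. Varying the block size among 4, 6 and 8 while the history stays visible still allows about 68% correct guesses. That is no better than fixed blocks of 6.

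**The case against.** The strongest reply is that the harm needs three things the document does not establish: a restricted list, recruiters who read the folder, and selective approach of patients. A reader might infer from section 7.3 that investigators can guess the next device. The text does not support that. Silence on the method is not evidence of a predictable sequence, and it is equally consistent with block sizes being deliberately withheld. This stands, and the point is conditional for that reason.

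A reader might also infer that the log stays in theatre. Section 7.3 says only that it is completed there; the envelopes alone are said to be kept. This stands too, but numbered envelopes by themselves reveal the history. Nor is theatre the place of recruitment: patients are approached at preoperative assessment with at least 2 hours to read the leaflet (sections 7.1.1 and 7.2). Even so, the document does not separate those who recruit from those who work in theatre.

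The larger error rates invite over-reading. A shift of ±0.25 SD is a 0.5 SD gap between patients expected to receive each device, and it is applied in full to intubation time. If the shift were in airway difficulty and only weakly related to time (correlation 0.3, an assumption), type I error would be about 6% to 8%. It would also be wrong to say that analysis cannot help. Section 7.5 records the airway assessment, and adjusting for a measured covariate on which selection acted restores about 5% in simulation. What remains is selection on unrecorded judgement, and the document prespecifies no such adjustment.

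Finally, operators remember their own cases, so moving the folder does not erase all history. That is true, but partial memory is far less informative than a complete ordered record (step 3).

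**Conclusion.** The point holds in a conditional form. Section 7.3 instructs that an ordered record of past allocations be kept in theatre with no access restriction, in a trial where the operator knows the device and recruiters may also work there. If the site lists use blocks of 2 to 6, a reader of the folder who knows the block size could guess about 68% to 75% of allocations, against 50% for an unrestricted list.

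The resulting bias cannot be fixed from the document. For assumed shifts of ±0.125 to ±0.25 SD in intubation time, type I error ranges from about 9–13% to about 22–38% for blocks of 6 to 2, before any adjustment for airway measures. If the lists are unrestricted, this harm is absent. The unstated sequence method alone would be a missing detail. What makes the point worth acting on is the explicit instruction to keep the envelopes in theatre, which is nearly free to change.

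**What to change.** Replace the last sentence of section 7.3 with wording such as: *After opening, each envelope and its log entry are passed promptly to the R&D office, or to another existing holder who neither recruits nor operates. No cumulative record of allocations is kept in theatre or made available to those who recruit.* The investigator site file is a weaker choice, because section 8.2 already places consent forms and CRFs there.

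If the lists are blocked, keep the block sizes varied and undisclosed to sites. This supplements removal of the visible history and does not replace it.

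Unrestricted lists are an option. Their mean efficiency is (180 × 179/4)/8,100 = 8,055/8,100 = 0.994, a loss of just over half a percent. The larger arm would be about 94 of 180 at the median and 103 at the 95th percentile.

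The cost is a sentence or two in section 7.3 and a small administrative step per patient. No extra patients are needed, and a new list is needed only if the sequence method is changed.

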### 7.5 Baseline data

Base line data includes gender, age, weight, height, BMI & ASA score

Airway assessment includes Mallampati score, thyromental distance, mouth opening and neck movement

### 7.6 Trial assessments

Time taken to insert supraglottic airway device  
Ease of SAD insertion and number of attempts  
View of the larynx through fiberoptic scope  
Time to view the carina (end of wind pipe)  
Total intubation time  
No of attempts  
Anaesthetist's visual analogue score on the ease of procedure  
Any additional manoeuvres required such as tube rotation or jaw thrust

## **8 DATA HANDLING**

### **8.1 Data collection tools and source document identification**

CRFs will completed at the time of data collection  
No other data collection is required

### **8.2 Data handling and record keeping**

Consent forms and CRFs will be filed into the investigator site file and the data is then entered at regular interval into the excel sheet on an encrypted NHS computer.

### **8.3 Access to Data**

Direct access will be granted to authorised representatives from the Sponsor, host institution and the regulatory authorities to permit trial-related monitoring, audits and inspections.

### **8.4 Archiving**

Research data will be stored off site in a secure approved NHS access facility - TNT. Only the research team will have authority to access this data if required via a request to the R&D Archiving Team. The study will be archived for 25 years from the close of the study with a review 1 year before the anticipated destruction date

## **9. TRIAL OVERSIGHT**

### **9.1 Role and responsibilities of the Sponsor**

UHCW has agreed to act as sponsor for this trial and will undertake the responsibilities of sponsor as defined by the Research Governance Framework and ICH Good Clinical Practice. An authorised representative of the Sponsor has approved the final version of this protocol with respect to the trial design, conduct, data analysis and interpretation and plans for publication and dissemination of results. As sponsor, UHCW provides indemnity for this trial and, as such, will be responsible for claims for any non-negligent harm suffered by anyone as a result of participating in this trial. The indemnity is renewed on an annual basis and will continue for the duration of this trial.

## **9.2 Principal Investigators**

“Site Principal Investigator responsibilities include, but are not limited to:

- Ensuring that the trial is conducted as set out in the protocol and supporting documents
- Delegating trial related responsibilities only to suitably trained and qualified personnel and ensuring that those with delegated responsibilities fully understand and agree to the duties being delegated to them;
- Ensuring that CVs and evidence of appropriate training for all Site staff are available in the Trial Site File
- Ensuring that all delegated duties are captured in the study Delegation Log
- Ensuring the trial is conducted in accordance with ICH GCP principles;
- Allowing access to source data for monitoring, audit and inspection;
- Ensuring that all source data is complete and provided to the chief investigator

## **10. MONITORING, AUDIT & INSPECTION**

The study will be monitored by the Research & Development department at UHCW as representatives of the Sponsor, to ensure that the study is being conducted as per protocol, adhering to Research Governance and GCP. The approach to, and extent of, monitoring will be specified in a trial monitoring plan determined by the risk assessment undertaken prior to the start of the study.”

## **11. ETHICAL AND REGULATORY CONSIDERATIONS**

### **11.1 Ethical approval and research governance**

The study will be conducted in compliance the principles of the ICH GCP guidelines and in accordance with all applicable regulatory guidance, including, but not limited to, the Research Governance Framework. Ethical approval for this study will be sought from the Research Ethics Committee combined with Health Research Authority (HRA) approval. No study activities will commence until favourable ethical opinion and HRA approval has been obtained. Progress reports and a final report at the conclusion of the trial will be submitted to the approving REC within the timelines defined by the committee. Confirmation of capacity and capability will be obtained from the R&D departments obtained prior to commencement of the study at all participating sites.

### **11.2 Peer review**

One external and internal review has been completed.

### **11.4 Data protection and patient confidentiality**

The study will comply with the Data Protection Act 1998. Participants will be assigned a unique identifier upon enrolment in to the study to allow link-anonymisation of patient-identifiable data. Access to patient identifiable data will be restricted to members of the study co-ordination team who require it for the performance of their role. Electronic data will be stored on password protected encrypted drives and hard copies of study documents will be stored in locked filing cabinets in secure entry-card protected sites.

## **12 DISSEMINATION POLICY**

The study finding will be first presented as an abstract at national meetings and subsequently published in Anaesthesia peer reviewed journal.

